24-hour UPEP and IFE	X	X (every cycle)	X	X (every cycle)
PB/Urine for mass spec l		X l (only if $\geq$ VGPR achieved)		X l (every cycle)
Quantitative Immunoglobulins	X	X (every cycle)	X	X (every cycle)
NT-proBNP, BNP, Troponin T & I m	X	X (every cycle)	X	X (every cycle)
Skeletal survey or CT scan	X			
Bone marrow biopsy n,o	X	X n (to confirm CR only)	X n	
Correlative Studies				
BM aspirate for MFC and NGS o	X	X o (only if $\geq$ VGPR achieved)	X o	
PET/MRI p	X	X p (only if $\geq$ VGPR achieved)	X p	

- a. Patients must sign the informed consent form before any study-specific procedures are performed
- b. During Cycle 1, patients will have clinic visit with physical exam with physician or advanced practice provider on Day 8, 15, and 22.
- c. Vital signs include temperature, heart rate, blood pressure
- d. On daratumumab infusion days on Day 1 and 8 of Cycle 1, vital signs will be measured before, during, and after daratumumab infusions. For all other infusions, vital signs will be measured before the infusion start and at the end of the infusion.
- e. Only if history of respiratory disease or active symptoms. Must include measurement forced expiratory volume at one second (FEV1)
- f. Not required if PET or chest CT scan has been obtained
- g. Diaries will be provided to patients to record self-administered pomalidomide and dexamethasone dosed at home. At Screening, the patient will receive instructions on how to complete the diary and it will subsequently be reviewed at each visit to evaluate compliance with pomalidomide and dexamethasone.
- h. See section 6.2.1.3 for pre- and post- daratumumab infusion medications
- i. Pregnancy test will be performed in female patients of childbearing potential at the following timepoints: 10-14 days before the first dose on C1D1; 24 hours before the first dose on C1D1; weekly for first 4 weeks of C1; monthly thereafter beginning with C2; EOT visit (serum or urine  $\beta$ -hCG). Non-child-bearing potential is defined as female patients who are permanently sterile or are post-menopausal (no menses in 12 consecutive months without an alternative medical cause).
- j. Serum chemistries: Albumin, alkaline phosphatase, total bilirubin, bicarbonate, BUN, calcium, chloride, creatinine, glucose, LDH, phosphorus, potassium, total protein, SGOT [AST], SGPT [ALT], sodium.

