#### Cycles 9-30 Maintenance (28-day cycle)

- Daratumumab 1800 mg SC q4wks on Day 1
- Pomalidomide 4 mg PO on Days 1-21 of 28-day cycle
- Dexamethasone 20 mg PO will be administered as a premedication prior to daratumumab injection on day 1 of daratumumab.
- Dexamethasone 20 mg PO weekly on non-daratumumab treatment days

During the study, assessments will be performed as shown in the Study Calendar and as clinically indicated.

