8. Females of childbearing potential (FCBP)† must have a negative serum or urine pregnancy test with a sensitivity of at least 25 mIU/mL within 10 – 14 days prior to and again within 24 hours of prescribing pomalidomide (prescriptions must be filled within 7 days) and must either commit to continued abstinence from heterosexual intercourse or begin TWO acceptable methods of birth control, one highly effective method and one additional effective method AT THE SAME TIME, at least 4 weeks before she starts taking pomalidomide FCBP must also agree to ongoing pregnancy testing. Men must agree to use a latex condom during sexual contact with females of child-bearing potential even if they have had a successful vasectomy. Females must agree not to donate eggs (ova, oocytes) and men not to donate sperm for the purpose of assisted reproduction during the study and for 4 weeks after the last dose of pomalidomide and for 3 months after the last dose of daratumumab. †A female of childbearing potential is a sexually mature woman who: 1) has not undergone a hysterectomy or bilateral oophorectomy; or 2) has not been naturally postmenopausal for at least 24 consecutive months (i.e., has had menses at any time in the preceding 24 consecutive months).
9. Able to take aspirin daily as prophylactic anticoagulation (patients intolerant to ASA may use warfarin or low molecular weight heparin).
10. Life expectancy  $\geq 3$  months
11. Subjects must meet the following laboratory parameters:

- i. Absolute neutrophil count (ANC)  $\geq 750$  cells/mm^3 ( $.75 \times 10^9/L$ )
- ii. Platelets count  $\geq 50,000/mm^3$  ( $50 \times 10^9/L$ )
- iii. Serum SGOT/AST  $\leq 2.0 \times$  upper limits of normal
- iv. Serum SGPT/ALT  $< 3.0 \times$  upper limits of normal (ULN)
- v. Serum CrCl  $\geq 30$  mL/min
- vi. Total bilirubin  $\leq 1.5 \times$  ULN (Total bilirubin  $\geq 1.5 \times$  ULN is acceptable if bilirubin is fractionated and direct bilirubin  $< 35\%$ ).
12. All study participants must be registered into the mandatory POMALYST REMS™ program and be willing and able to comply with the requirements of the POMALYST REMS™ program.

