### **Embryo-Fetal Toxicity**

Pomalidomide is a thalidomide analogue and is contraindicated for use during pregnancy. Thalidomide is a known human teratogen that causes severe birth defects or embryo-fetal death. pomalidomide is only available through the pomalidomide REMS program.

Females of Reproductive Potential Females of reproductive potential must avoid pregnancy for at least 4 weeks before beginning pomalidomide therapy, during therapy, during dose interruptions and for at least 4 weeks after completing therapy.

Females must commit either to abstain continuously from heterosexual sexual intercourse or to use 2 methods of reliable birth control, beginning 4 weeks prior to initiating treatment with pomalidomide, during therapy, during dose interruptions, and continuing for 4 weeks following discontinuation of pomalidomide therapy. Two negative pregnancy tests must be obtained prior to initiating therapy. The first test should be performed within 10-14 days and

the second test within 24 hours prior to prescribing pomalidomide therapy and then weekly during the first month, then monthly thereafter in females with regular menstrual cycles, or every 2 weeks in females with irregular menstrual cycles.

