#### Pregnancy Testing

Pomalidomide can cause fetal harm when administered during pregnancy.

Verify the pregnancy status of females of reproductive potential prior to initiating pomalidomide therapy and during therapy. Advise females of reproductive potential that they must avoid pregnancy 4 weeks before therapy, while taking pomalidomide, during dose interruptions and for at least 4 weeks after completing therapy.

Females of reproductive potential must have 2 negative pregnancy tests before initiating pomalidomide. The first test should be performed within 10-14 days, and the second test within 24 hours prior to prescribing pomalidomide. Once treatment has started and during dose interruptions, pregnancy testing for females of reproductive potential should occur weekly during the first 4 weeks of use, then pregnancy testing should be repeated every 4 weeks in females with regular menstrual cycles. If menstrual cycles are irregular, the pregnancy testing should occur every 2 weeks. Pregnancy testing and counseling should be performed if a patient misses her period or if there is any abnormality in her menstrual bleeding. Pomalidomide treatment must be discontinued during this evaluation.

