### **7.2 Treatment Period**

Clinical evaluations and laboratory assessments will be performed as per the Schedule of Study Procedures and as clinically indicated.

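### Schedule footnote i is less protective on pregnancy testing than inclusion criterion 8 (12 versus 24 months without menses) and Section 6.6 (no two-weekly tests for irregular cycles), and nothing says which text governs

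*Combined protocol and SAP*

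**What the plan says.** Footnote i limits pregnancy testing to women of childbearing potential. It excludes women who are permanently sterile (a term it does not define) or "post-menopausal (no menses in 12 consecutive months without an alternative medical cause". For those tested, it sets one test 10 to 14 days before the first dose, then "24 hours before the first dose on C1D1; weekly for first 4 weeks of C1; monthly thereafter beginning with C2", then one at the end-of-treatment visit. It has no branch for irregular cycles and does not refer to Section 6.6.

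Inclusion criterion 8 (Section 5.1) defines a woman of childbearing potential as one who has had neither a hysterectomy nor a bilateral oophorectomy, or who "has not been naturally postmenopausal for at least 24 consecutive months". Such a woman needs two negative baseline tests, must be abstinent or use two contraceptive methods, and must agree to continued testing.

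Section 6.6 gives the on-treatment frequency twice. Embryo-Fetal Toxicity has weekly tests in the first month, then monthly tests with regular cycles "or every 2 weeks in females with irregular menstrual cycles". Pregnancy Testing agrees: "If menstrual cycles are irregular, the pregnancy testing should occur every 2 weeks". It adds an event trigger: "Pregnancy testing and counseling should be performed if a patient misses her period", or if bleeding is abnormal.

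Section 4.1 says "assessments will be performed as shown in the Study Calendar and as clinically indicated". Section 7.2 says "Clinical evaluations and laboratory assessments will be performed as per the Schedule of Study Procedures and as clinically indicated".

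**The concern.** The calendar is the part of the protocol that sites are told to work from, and here it disagrees with the body text on who is tested and how often. A woman whose last natural period was between 12 and 24 months ago is of childbearing potential at eligibility but outside the testing group in the calendar. A woman with irregular cycles is scheduled every 28 days in one place and every 14 days in another. Both differences make the calendar the weaker text, and both concern women near menopause.

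Section 6.6 contraindicates pomalidomide in pregnancy and describes it as an analogue of a known human teratogen. A longer gap between tests could delay detection of a pregnancy while dosing continues on days 1 to 21. The Protocol Summary lists three enrolling facilities, so different staff could resolve the conflict differently. This is a matter of participant safety and protocol consistency, not of inference.

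**Working it through.** The plan gives no figure to reproduce. The check compares the texts and counts scheduled tests.

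**Who is tested.** The thresholds are 12 months (footnote i) and 24 months (inclusion 8), a gap of 24 − 12 = 12 months. Within it a woman is in the testing group under one text and outside it under the other. The surgical exemptions also differ in wording. Footnote i leaves permanent sterility undefined, whereas inclusion 8 names only hysterectomy and bilateral oophorectomy. Section 6.6 lists tubal ligation as a contraceptive method, so a woman with a ligation could be classified either way.

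**How often, irregular cycles.** Assumptions: 28-day cycles, first dose on day 0, no delays, 1 month = 30.44 days, and first post-cycle-1 test on day 28. For treatment length T in days:
- monthly tests = floor((T − 28)/28) + 1
- two-weekly tests = floor((T − 28)/14) + 1
- for n whole cycles: n − 1 and 2(n − 1)

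The documents do not predict treatment length for this regimen, so a range is shown:
- 5 cycles is the median number of treatment cycles in both pomalidomide trials in Section 1.4.2.
- 7.7 and 8.8 months are the median PFS values in Section 1.1 for ClaPd and for daratumumab/pomalidomide/dexamethasone. Both come from other regimens and populations.
- 30 cycles is the maximum in Section 4.3.

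For 7.7 months, T = 7.7 × 30.44 = 234.4. Then 206.4/28 = 7.37 gives 8 tests, and 206.4/14 = 14.74 gives 15. For 8.8 months, T = 267.9. Then 239.9/28 = 8.57 gives 9, and 239.9/14 = 17.1 gives 18.

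| Treatment length | Footnote i | Section 6.6 | Extra tests | Extra tests in cycle 7 or later |
|---|---|---|---|---|
| 5 cycles | 4 | 8 | 4 | 0 |
| 7.7 months | 8 | 15 | 7 | 2 |
| 8.8 months | 9 | 18 | 9 | 4 |
| 30 cycles | 29 | 58 | 29 | 24 |

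The last column matters for cost. In the Schedule, dosing and routine blood tests fall on days 1, 8, 15 and 22 in cycle 2 and on days 1 and 15 in cycles 3 to 6, but on day 1 only from cycle 7. The mid-cycle test in cycle n falls on day 28(n − 1) + 14: day 182 for cycle 7, then 210, 238 and 266 for cycles 8 to 10. Two of these fall by day 234 and four by day 268. Over 30 cycles there are 30 − 6 = 24.

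**Tests at stake in the 12–24 month band.** Inclusion 8 gives no frequency for ongoing testing, so footnote i's own frequency is assumed: 4 weekly tests in cycle 1, then monthly. Baseline tests are left out because inclusion 8 requires them. If status is fixed at entry:
- 5 cycles: 4 + 4 = 8
- 7.7 months: 4 + 8 = 12
- 8.8 months: 4 + 9 = 13
- 30 cycles: 4 + 29 = 33

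The end-of-treatment test is extra in each case. If status is reassessed and treatment continues, testing stops when she reaches 24 months. A woman entering at 12 months (band ends about day 365) has 4 + 13 = 17 tests at stake, and one entering at 23 months (about day 30) has 4 + 1 = 5. The protocol does not say whether status is reassessed.

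**The case against.** The frequency point is closer to an omission than a contradiction. Footnote i gives a general schedule, Section 6.6 supplies the special case, and the clinical-indication clause in Sections 4.1 and 7.2 lets a site follow both. That largely stands, but the clause permits extra tests without telling anyone that the two-weekly rule or the 24-month definition applies.

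The definition point affects a narrow group. Footnote i's exemption already excludes amenorrhoea with another medical cause, so a reader should not infer that women with treatment-induced amenorrhoea go untested. To skip tests for the remaining women, a site would have to treat a patient as of childbearing potential at eligibility and then reclassify her from a footnote. This too stands: missed tests are an inference about conduct. REMS registration and compliance are mandatory under inclusion 12, but the documents do not state the REMS testing rules, so REMS cannot be assumed to correct the footnote.

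Two stronger readings are not supported:
- That two-weekly testing is an absolute requirement which the calendar breaches. Section 6.6 says it should occur.
- That footnote i's test 24 hours before the first dose conflicts with the test within 24 hours of prescribing in inclusion 8 and Section 6.6. Both can be done.

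**Conclusion.** The inconsistency is real and present in the current text. The calendar uses a definition 12 months shorter than the eligibility criterion and, for irregular cycles, half the per-cycle test frequency that Section 6.6 advises from cycle 2. Nothing says which text prevails. The counts rest on undelayed 28-day cycles and on borrowed treatment lengths, so they illustrate scale only.

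The documents do not give the number of women affected. It is probably small, with 40 patients and a cited median age of 69 for myeloma. A reader might infer that women on this trial are left unprotected or that sites will miss tests. The documents do not support that, because the baseline tests, contraception rules, missed-period trigger and REMS all remain. Sample size, the primary endpoint and its analysis are unaffected. The correction is worth making because the calendar, as written, is the less safe of two conflicting instructions.

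**What to change.** Amend footnote i:

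- **(a)** Replace its definition of non-childbearing potential with that of inclusion 8: hysterectomy or bilateral oophorectomy, or naturally postmenopausal for at least 24 consecutive months. This also settles the undefined sterility term, and the word *naturally* keeps women with treatment-induced amenorrhoea in testing.
- **(b)** After the monthly rule from cycle 2, add two-weekly testing where menstrual cycles are irregular, with a cross-reference to Section 6.6.
- **(c)** Optionally, list the test within 24 hours of prescribing alongside the pre-dose test, which stays. This is harmonisation, not correction of a conflict.

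The drafting cost is one footnote. For a woman with irregular cycles, the cost is 1 extra test per cycle from cycle 2, plus one mid-cycle contact per cycle from cycle 7, when scheduled visits fall on day 1 only. For a woman in the 12–24 month band it is the 4 tests in cycle 1 and 1 per later cycle, plus the end-of-treatment test if she is still in the band then. Option (c) adds one pre-treatment test if prescribing and first dose are more than 24 hours apart.

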## LIST OF ABBREVIATIONS AND GLOSSARY OF TERMS

*Common abbreviations used in oncology protocols are provided below. Program-specific or protocol-specific abbreviations must be added to this list, and unnecessary abbreviations removed, as applicable. Abbreviations that are retained should not be changed.*

Abbreviation	Term
ADR	adverse drug reaction
AE	adverse event
ALP	alkaline phosphatase
ALT	alanine aminotransferase
ANC	absolute neutrophil count
aPTT	activated partial thromboplastin time
AST	aspartate aminotransferase
AUC	area under the plasma concentration versus time curve
AUC 24 hr	area under the plasma concentration versus time curve from zero to 24 hours
AUC inf	area under the plasma concentration versus time curve from zero to infinity
AUC τ	area under the plasma concentration versus time curve from zero to next dose
BCRP	breast cancer resistance protein
βhCG	beta-human chorionic gonadotropin
BID	bis in die; twice a day
BM	bone marrow
BSA	body surface area
BUN	blood urea nitrogen
CBC	complete blood count
CL	clearance, IV dosing
CL P	plasma clearance
CL Total	total clearance
C max	single-dose maximum (peak) concentration
CNS	central nervous system
CO 2	carbon dioxide
CR	complete response
CRM	continual reassessment method
CT	computed tomography
C trough	single-dose end of dosing interval (trough) concentration
CV	coefficient of variation
CYP	cytochrome P 450
DI d	Daratumumab, Ixazomib, dexamethasone

Abbreviation	Term
DDI	drug-drug interaction
DLT	dose-limiting toxicity
DME	drug metabolizing enzymes
DNA	deoxyribonucleic acid
ECG	Electrocardiogram
ECOG	Eastern Cooperative Oncology Group
eCRF	electronic case report form
EDC	electronic data capture
ELISA	enzyme-linked immunosorbent assay
EOS	End of Study (visit)
EOT	End of Treatment (visit)
FDA	United States Food and Drug Administration
GCP	Good Clinical Practice
G-CSF	granulocyte colony stimulating factor
GGT	gamma glutamyl transferase
GI	Gastrointestinal
GLP	Good Laboratory Practices
GM-CSF	granulocyte macrophage-colony stimulating factor
GMP	Good Manufacturing Practice
Hb	Hemoglobin
Hct	Hematocrit
HDPE	high-density polyethylene
HIV	human immunodeficiency virus
IB	Investigator's Brochure
IC 50	concentration producing 50% inhibition
ICF	informed consent form
ICH	International Conference on Harmonisation
IEC	independent ethics committee
IRB	institutional review board
ITT	intent-to-treat
IV	intravenous; intravenously
K i	inhibition constant
LDH	lactate dehydrogenase
LFT	liver function test(s)

Abbreviation	Term
MedDRA	Medical Dictionary for Regulatory Activities
Millennium	Millennium Pharmaceuticals, Inc., and its affiliates
MM	Multiple Myeloma
MRI	magnetic resonance imaging
MRU	medical resource utilization
MTD	maximum tolerated dose
MUGA	multiple gated acquisition (scan)
NCCN	National Comprehensive Cancer Network
NCI	National Cancer Institute
NCI CTCAE	National Cancer Institute Common Terminology Criteria for Adverse Events
NPO	nothing by mouth
NT-proBNP	N-terminal pro b-type natriuretic peptide
NYHA	New York Heart Association
OS	Overall survival
PBMC	peripheral blood mononuclear cell
PCR	polymerase chain reaction
PD	progressive disease (disease progression)
PFS	Progression free survival
Pgp	P-glycoprotein
PK	pharmacokinetic(s)
PO	per os ; by mouth (orally)
PR	partial remission or partial response choose one
PRO	patient-reported outcome
QD	quaque die ; each day; once daily
QID	quater in die ; 4 times a day
QOD	quaque altera die ; every other day
QOL	quality of life
QTc	rate-corrected QT interval (millisec) of electrocardiograph
RBC	red blood cell
SAE	serious adverse event
SC	Subcutaneous
SD	stable disease
SmPC	Summary of Product Characteristics
t 1/2	terminal disposition half-life
TEAE	treatment-emergent adverse event

Abbreviation	Term
TGI	tumor growth inhibition
T max	single-dose time to reach maximum (peak) concentration
ULN	upper limit of the normal range
US	United States
V z	volume of distribution in the terminal phase
VGPR	Very good partial response
WBC	white blood cell
WHO	World Health Organization

# 1. BACKGROUND AND STUDY RATIONALE

## 1.1 Scientific Background and Study Rationale

Multiple Myeloma (MM) is a neoplastic disorder characterized by abnormal proliferation of plasma cells producing excess quantities of single immunoglobulin protein isotype (M-protein). It is estimated that 19,000 new cases of myeloma are diagnosed in the US each year, accounting for approximately 1% of all cancers and 10-15% of all hematological malignancies. The disease is twice as common in blacks as whites. MM usually occurs in older individuals with a median age of 69 years old.

The overall median survival for patients with MM is 36 months, with stage I, II, and III patients surviving a median of >60, 41, and 23 months respectively. Several prognostic factors have been identified. An elevated serum level of beta-2 micro-globulin ( $\beta$ 2M), a component of the class I HLA molecule, is a powerful prognostic indicator of shortened survival. Since  $\beta$ 2M is excreted by the kidney, renal insufficiency will increase serum levels of  $\beta$ 2M. The plasma cell labeling index (PCLI) identifies the percentage of proliferating plasma cells in S phase of the cell cycle and is powerful independent predictor of progression and survival. An elevated serum lactate dehydrogenase (LDH) predicts an aggressive course with lymphoma like features. Chromosomal abnormalities, such as translocations t(4;14) and t(14;16) confer poor prognosis.

Patients who have previously been treated for myeloma and have relapsed, or patients that have MM that is refractory to therapy, are known to have a worse overall prognosis in terms of survival, likelihood of response to other chemotherapeutics, as well as duration of response to salvage therapies. MM is still an incurable disease and all patients eventually relapse or become refractory to treatment. There are few salvage therapies available, so it is imperative to investigate new treatment options for the MM patients with relapsed or refractory disease.

The emergence of immunomodulatory drugs (IMiDs), such as thalidomide, lenalidomide and pomalidomide, as effective therapies have altered the therapeutic paradigm for MM. Following the approval and establishment of thalidomide-containing regimens, such as melphalan, prednisone and thalidomide (MPT) as the standard first-line therapy for newly diagnosed MM (NDMM), lenalidomide in combination with standard high-dose dexamethasone (RD) was approved for the treatment of patients with previously treated and NDMM. Pomalidomide is an analogue of thalidomide that, among other anti-tumor properties, on an equimolar basis *in vitro*, displays equivalent anti-angiogenic activity, about 8-fold greater activity in stimulation of apoptosis, at least 10-fold greater activity in inhibition of cellular COX-2 production and over 4,000-fold greater activity in inhibition of cellular TNF-alpha production relative to thalidomide. Pomalidomide has also been shown to stimulate antibody-dependent cytotoxic T-cell activity (ADCC).

However, even with the newly approved agents including thalidomide, lenalidomide and proteasome inhibitors such as bortezomib and carfilzomib, MM remains an incurable disease and most patients will eventually relapse and progress after multiple lines of different therapeutic regimens.

At tolerated doses (MTD = 2 mg QD and 5 mg QOD), pomalidomide has been shown to be active in subjects with relapsed or refractory MM (study CC-4047-00-01). In 45 subjects who received doses of pomalidomide ranging, by cohort, up to 10 mg daily, the most commonly occurring dose-limiting toxicity (DLT) was reversible neutropenia. As with other IMiDs administered to subjects receiving concomitant systemic steroids, deep vein thrombosis (DVT) was seen. Pivotal phase 2 and 3 studies of pomalidomide/ dexamethasone in relapsed/refractory MM yielded ORRs of 33% and 31%, respectively. In a randomized phase 2 study, pomalidomide with/without low-dose dexamethasone in patients with relapsed/refractory multiple myeloma was assessed. Patients who had received  $\geq 2$  prior therapies including lenalidomide and bortezomib were randomized to POM (4 mg/day on days 1-21 of each 28-day cycle) with/without dexamethasone (40 mg/week). In the pomalidomide/ dexamethasone arm, median PFS was 4.2 months, ORR was 33%, CR 3%, median response duration was 8.3 and median overall survival 16.5. Grade 3-4 neutropenia occurred in 41%; no grade 3-4 peripheral neuropathy was reported. In a phase 3 study (5 median prior lines, 100% lenalidomide/ bortezomib exposed, 95% lenalidomide refractory and 75% double-refractory), ORR 31%,  $\geq$ VGPR 6% and  $\geq$ CR 1%. At a median f/u of 10 mos, median PFS 4 mos and median OS 12.7 mos. The most common grade 3-4 haematological adverse events in the pomalidomide plus low-dose dexamethasone was neutropenia 48%, anaemia 33%, and thrombocytopenia 22%. Grade 3-4 non-haematological adverse events in the pomalidomide plus low-dose dexamethasone included pneumonia 13%, bone pain 7%, and fatigue 5%. There were 4% treatment-related adverse events leading to death in the pomalidomide plus low-dose dexamethasone group.

Daratumumab, both as monotherapy and in combination, appears safe and highly effective in heavily pretreated MM and is approved as a single agent for patients who have received at least three prior lines of therapy including a proteasome inhibitor and an immunomodulatory drug or who are double-refractory to a proteasome inhibitor and an immunomodulatory drug. In an open-label, international, phase 2 trial (SIRIUS), 106 patients with relapsed MM (median of five prior therapies) were treated with daratumumab (16 mg/kg, weekly for eight weeks and then every two weeks for 16 weeks). Infusion reactions, mostly mild, were common with the first infusion (37 %) and occurred in 6% of subsequent infusions. The ORR was 29 % ( $\geq$ VGPR 12%, CR 3%) with a median time to first response of one month. The estimated median PFS and OS rates were 3.7 and 17.5 months, respectively.

A favorable toxicity profile makes daratumumab a particularly good combination agent. The safety of an IMiD with daratumumab, even in patients previously exposed yields very low toxicity and good efficacy. Combination studies of lenalidomide and pomalidomide with daratumumab at various dose levels has been studied in the daratumumab naïve relapsed/refractory myeloma setting. Daratumumab 16 mg/kg plus pomalidomide (4 mg days 1-21) and dexamethasone 40 mg weekly (DPd) in a 28-day cycle was evaluated in 103 relapsed/refractory myeloma patients with median of 4 prior therapies. ORR was 60%,

≥VGPR 42%, and MRD+ was 29% in the CR patients. Median PFS was 8.8 mos. Aside from increased neutropenia (grade ≥3 neutropenia 78% without increased infection rate), the safety profile of DPd was consistent with that of the individual therapies.

Pomalidomide and daratumumab combination have been shown to potentiate clinical efficacy in myeloma even when the disease has developed resistance to the individual agents. Patients with pomalidomide and/or daratumumab-refractory disease were identified who were treated with daratumumab-pomalidomide/dexamethasone. Of the 11 refractory to either daratumumab or pomalidomide, the ORR and CBR were 54·6% (all PRs) and 63·6%. Of the 8 refractory to both daratumumab and pomalidomide in separate lines of therapy, ORR and CBR were 12·5% (all PRs) and 50·0%. Nooka *et al* also reported an ORR with daratumumab-pomalidomide of 36·8% in patients with daratumumab or pomalidomide-refractory disease and 33·3% for those with daratumumab and pomalidomide-refractory disease.

Biaxin®, or clarithromycin, is a semi-synthetic macrolide antibiotic indicated for the treatment of mild to moderate infections caused by susceptible strains of microorganisms. Pre-clinical studies have shown that Biaxin® has immunomodulatory properties mediated in part by suppression of Interleukin-6 and other cytokines and slows hepatic clearance of dexamethasone leading to greater corticosteroid exposure. Based upon these properties, the group at Cedars Sinai Comprehensive Cancer Center began a trial using Biaxin® 500mg bid for the treatment of newly diagnosed and relapsed/refractory MM patients. Of the 30 patients treated, 6 patients achieved a CR, 7 achieved a PR, 6 patients had SD, 4 had a mixed response and 7 patients were too early to evaluate. Follow up studies by other groups in Canada and France have failed to duplicate these promising results.

A phase II study of clarithromycin (500mg twice daily), lenalidomide (25mg daily for 21 days out of a 28 day cycle), and dexamethasone (40mg weekly) called the BiRD regimen was conducted at this institution. We achieved an overall response rate of 91%, and CR rate of 30%. The BiRD study evaluated the efficacy of the combination of Biaxin®, lenalidomide, and dexamethasone in treatment-naïve MM patients and proved to be a powerful regimen.

In the relapsed/refractory setting, a Phase 2 study of Biaxin®, pomalidomide, and dexamethasone (ClAPd) was studied in 120 patients with median of 5 prior lines (84% lenalidomide refractory). An ORR of 60% with ≥VGPR 23%, median PFS and DoR 7.7 and 9.3 mos, respectively and median OS 19.3 mos was seen. No influence on PFS was seen with lenalidomide or lenalidomide/bortezomib refractoriness nor significant differences in PFS/OS between low and high-risk patients. The most common gr 3/4 AEs were neutropenia 47% (gr 4 14%), lymphopenia 37% (gr 4 6%) and thrombocytopenia 33% (gr 4 16%) with no grade 5 events and a discontinuation rate of 3%.

This study is intended to investigate the combination of daratumumab, clarithromycin (Biaxin®), pomalidomide and dexamethasone [D-ClAPd] in multiple myeloma patients who have relapsed or refractory MM and have been previously exposed to daratumumab. Primary

endpoint will be response rate to treatment. Secondary endpoints will include toxicity of the combination, time to maximum response, and time to disease progression.

